## **REQUOL Study**

**Treatment Satisfaction:** Arithmetical mean of the scores of items 4, 12, 14, 15, 21 and 27 (the results of each item in this dimension must be inverted:  $n+1$ -score of the item,  $n$  is the number of scales, in this case  $n=6$ )

**Self-efficacy:** Arithmetical mean of the scores of items 5, 9, 18 and 24

**Stress:** Arithmetical mean of the scores of items 1, 8, 10, 13, 19, 25, 26, 28, 30, 31

**Limitations:** Arithmetical mean of the scores of items 2, 3, 6, 7, 11, 22, 23

**Social disturbances :** Arithmetical mean of the scores of items 16, 17, 20, 29, 32

The descriptive statistic (Mean, SD, Median,  $Q_1$ ,  $Q_3$ , Min, Max) will be shown for each of the questionnaire's items (in the inverted items, the inverted value will be provided):

1. My treatment makes me feel worried or stressed
2. The effort of controlling my blood clotting causes me discomfort when I leave the house
3. My treatment prevents me from organising my leisure time how I wish
4. I am dissatisfied with the amount of time I invest in controlling my clotting
5. I believe I have learned to control my treatment
6. The risk of cutting myself prevents me from performing housework
7. I avoid some activities (e.g. Cycling) due to the risk of accidents
8. My treatment is a cause of concern for my family
9. I can deal with the treatment-related problems that arise
10. I am worried about my future health
11. I am afraid of doing exercise for fear that I will hurt myself
12. I am dissatisfied with the time it takes to get results
13. I am worried that my treatment may shorten my life
14. I dislike having to plan my activities in advance
15. I am worried by the uncertainty I feel while awaiting results
16. I see my friends less since following this treatment
17. I avoid going on holiday because I do not know the negative effects different foods may have on my treatment
18. I am well informed about what to do to achieve results within the acceptable limits
19. I feel dependent on my anticoagulation medication
20. I avoid travelling because I fear that I may not receive suitable treatment in case my results are too low or high
21. I am fed up with the amount of time I lose at the doctor's surgery
22. I would do more sports if I did not take anticoagulants
23. I have problems at work because of frequent absences caused by my treatment
24. I am sure I am able to control my treatment
25. I tend to worry about things

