## **7. RATIONALE AND BACKGROUND**

Atrial fibrillation (AF) affects 1-2% of general population, but specially persons between 80 - 85 years, in whom the prevalence can reach 16% [1-3]. The first oral anticoagulants to prevent the risk of thromboembolic events in AF were the vitamin K antagonists (VKA) warfarin and acenocoumarol. The management of these agents remains problematic because they need routine coagulation monitoring, clinical surveillance and continuous patient education, affecting to their daily habits and in consequence to their quality of life [4]. Also, data show that 80% of patients continue receiving acenocoumarol in Spain, with a percentage of International Normalized Ratio (INRs) in therapeutic range between 44%-59% [5,6], and mean time in therapeutic range (TTR) of 64% [5].

The direct oral anticoagulants (DOAC) maintain the benefits of anticoagulant therapy and may increase perception of quality of life among patients because they not necessitate the strict monitoring required for VKA. On the other hand maintaining a stable level of anticoagulation with DOACs prevents uncontrolled patients as well as the increased number of monitoring visits for this reason. Theoretically, this fact would have positive implications in quality of life. However, the available evidence from the study of quality of life, does not suggest that patients have large decrements in their quality of life because of suffering from FA. In this sense, the study of Roalfe et al., cross sectional in 1762 patients over 75 years and suffering AF, concluded that in absence of comorbidity, chronic AF has little impact on generic QoL [7]. This suggests that treatment strategies should focus on the prevention of complications such as stroke, so it is necessary to go depth in the study of the anticoagulant therapy and the impact in QoL.

HRQoL was assessed in a sub-group of the overall RE-LY population to measure the effect of the choice of anticoagulant during a stable phase of treatment in the first year of the study, in patients without outcome events, such as strokes or major bleedings [8]. HRQoL was assessed using the EQ-5D, a generic measure of health outcome. Over the course of one year, all anticoagulated patients without outcome events had stable HRQoL. Scores between dabigatran and warfarin were comparable. There is a dearth of evidence regarding HRQoL in controlled and uncontrolled patients on oral anticoagulants.

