## **9.9 LIMITATIONS OF THE RESEARCH METHODS**

This study is only descriptive and is not designed to allow for causal inference regarding the impact of OAC control on HRQoL.

Apart from inherent limitations of observational studies, a criticism could be the use of a specific questionnaire of HRQoL originally designed for patients receiving oral anticoagulation with vitamin K and that could ignore other aspects related to quality of life in atrial fibrillation as previously reported

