## **ANNEX 3. ADDITIONAL INFORMATION**

### **Spanish adaptation of the Sawicki questionnaire:**

1. Su tratamiento le hace sentir preocupado o estresado	1	2	3	4	5	6
2. El esfuerzo por controlar su coagulación sanguínea le produce molestias cuando está fuera de casa	1	2	3	4	5	6
3. Su tratamiento le limita para organizar su tiempo libre como quiere	1	2	3	4	5	6
4. Está insatisfecho con la cantidad de tiempo que invierte en controlar su coagulación	1	2	3	4	5	6
5. Cree que ha aprendido a controlar su tratamiento	1	2	3	4	5	6
6. El riesgo de hacerse heridas le limita para llevar a cabo sus tareas domésticas	1	2	3	4	5	6
7. Evita realizar ciertas actividades (p. ej. Montar en bicicleta) por el riesgo de accidentes	1	2	3	4	5	6
8. Su tratamiento preocupa a sus familiares	1	2	3	4	5	6
9. Puede afrontar los problemas que surgen relacionados con su tratamiento	1	2	3	4	5	6
10. Le preocupa su salud en el futuro	1	2	3	4	5	6
11. Tiene miedo de realizar ejercicio por el miedo de hacerse una herida	1	2	3	4	5	6
12. Está insatisfecho con el tiempo que le lleva conseguir los resultados	1	2	3	4	5	6
13. Le preocupa que su tratamiento pudiera acortar su vida	1	2	3	4	5	6
14. Le disgusta tener que planear sus actividades con antelación	1	2	3	4	5	6
15. Le preocupa la incertidumbre que siente mientras espera los resultados	1	2	3	4	5	6
16. Ve menos a sus amigos desde que sigue este tratamiento	1	2	3	4	5	6
17. Evita salir de vacaciones porque es incapaz de conocer los efectos negativos que tienen los diferentes alimentos en su tratamiento	1	2	3	4	5	6
18. Está bien informado de lo que debe hacer para conseguir unos resultados dentro de los límites adecuados	1	2	3	4	5	6
19. Se siente dependiente de su medicación anticoagulante	1	2	3	4	5	6
20. Evita viajar porque tiene miedo de no recibir tratamiento adecuado en el caso de que sus resultados estén demasiado altos o bajos	1	2	3	4	5	6

Proprietary confidential information © 2017 Boehringer Ingelheim International GmbH or one or more of its affiliated companies

21. Está harto de la cantidad de tiempo que pierde en el médico	1	2	3	4	5	6
22. Practicaría más deporte si no tomara anticoagulantes	1	2	3	4	5	6
23. Tiene problemas en el trabajo por sus frecuentes faltas a causa del tratamiento	1	2	3	4	5	6
24. Está seguro de poder controlar su tratamiento	1	2	3	4	5	6
25. Tiende a preocuparse por las cosas	1	2	3	4	5	6
26. A pesar de las visitas habituales al médico, cómo se siente de limitado	1	2	3	4	5	6

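### Six Sawicki items about clotting control or test results may not apply to the DOAC patients in the controlled group, and SAP 8.1 makes no provision for this

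*SAP*

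**What the plan says.** The primary outcome is the Sawicki questionnaire, 32 items in five dimensions. Under SAP 8.1 the Treatment Satisfaction score is the "Arithmetical mean of the scores of items 4, 12, 14, 15, 21 and 27", with every item inverted. The other four scores are plain item means without inversion: Self-efficacy has four items (18 among them), Stress ten, Limitations seven (2 among them) and Social disturbances five (20 among them).

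Answers run from 1 (*Nada*) to 6 (*Mucho*) in Protocol Annex 3. Neither document offers a not-applicable answer. Several items take clotting control or a test result for granted. Item 12, for example, reads "Está insatisfecho con el tiempo que le lleva conseguir los resultados".

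Protocol 7 says of DOACs that "they not necessitate the strict monitoring required for VKA". Protocol 9.2 and SAP 5.1 place every DOAC patient in the controlled group, together with VKA patients whose TTR is adequate; the uncontrolled group is VKA only. SAP 8.1 reports items and dimensions for the controlled, uncontrolled and total populations, without a DOAC/VKA split.

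Protocol 9.9 acknowledges that the questionnaire was built for VKA users. The limitation it draws is that the instrument "could ignore other aspects related to quality of life in atrial fibrillation". That concerns missing content, not items that do not apply.

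**The concern.** A patient who has no clotting test cannot sensibly rate the wait for its result or say how well informed he or she is about keeping it in range. The form still leaves only two choices: tick a number or leave a blank. Because DOAC patients appear in one group only, any effect of such answers falls on one side of the planned description. Part of a difference between the two columns could then come from who can meaningfully answer the items rather than from anticoagulation control, which is what the columns are meant to describe. The planned tables would not let a reader tell these apart.

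Item 18 is the clearest case. It is positively worded, so *Nada* from someone with no results to manage is scored like *Nada* from someone who does not know how to manage them.

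**Working it through.** **1. Structure.** The dimensions in SAP 8.1 hold 6 + 4 + 10 + 7 + 5 = 32 items, each used once. The stated 32 items in five dimensions reproduce.

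**2. Affected items.** Read from the item wording in SAP 8.1 and Protocol Annex 3, items 2 and 4 concern controlling clotting, and items 12, 15, 18 and 20 concern results.

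**3. Shift for one DOAC patient.** Let k of the t items in a dimension be affected, and let m be the raw answer the patient would give if the items applied. A floor answer of 1 moves the dimension score by k(m − 1)/t. Inversion (7 − answer) changes the sign, not the size. The documents contain no item data, so m = 2 to 4 is an assumption.

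**4. Shift in the controlled-group mean.** Multiply by q, the DOAC share of the controlled group: q·k(m − 1)/t. The documents do not fix q; 25-75% is assumed.

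| Dimension | Items | k/t | One patient, m = 2, 3, 4 | Group mean, lowest to highest |
|---|---|---|---|---|
| Treatment Satisfaction | 4, 12, 15 | 3/6 | 0.50, 1.00, 1.50 | 0.25 × 0.50 = 0.13 to 0.75 × 1.50 = 1.13 |
| Self-efficacy | 18 | 1/4 | 0.25, 0.50, 0.75 | 0.06 to 0.56 |
| Social disturbances | 20 | 1/5 | 0.20, 0.40, 0.60 | 0.05 to 0.45 |
| Limitations | 2 | 1/7 | 0.14, 0.29, 0.43 | 0.04 to 0.32 |
| Stress | none | 0/10 | 0 | 0 |

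With q = 0 every shift is zero.

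**5. Narrower item set.** Counting only the four items that mention results, Treatment Satisfaction falls to 2/6 and Limitations drops out. The Treatment Satisfaction range becomes 0.25 × (2/6) × 1 = 0.08 to 0.75 × (2/6) × 3 = 0.75.

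**6. Scale for comparison.** For groups of 330 and 170, the 95% half-width of a difference in means is 1.96 × SD × √(1/330 + 1/170) = 0.185 × SD, or 0.19 to 0.28 at an assumed SD of 1.0 to 1.5. No test is planned, so this is only a yardstick. Much of the Treatment Satisfaction range exceeds it; the low end does not.

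**7. Direction.** SAP 8.1 says that the highest scores mean poorer quality of life. It also inverts Treatment Satisfaction, so a floor answer on items 4, 12 and 15 becomes 6 and raises that score. Self-efficacy is not inverted although its items are positively worded, so a floor answer on item 18 lowers it. Under the general rule the first shift reads as worse and the second as better; by item content both readings reverse. Limitations and Social disturbances fall, which reads as better either way.

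**8. Blanks.** Protocol 9.7 rules out imputation, and SAP 8.1 divides by the count of items in the dimension without setting a minimum number answered. If 4, 12 and 15 are blank, the Treatment Satisfaction score could be missing, averaged over three items, or divided by six, which is half the three-item value.

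**The case against.** The strongest reply is that a low answer may be true. Protocol 7 expects VKA monitoring to burden daily life and DOACs to relieve that burden, and Protocol 9.3.2.1 defines the outcome as self-perceived, treatment-related quality of life. A DOAC patient who reports no dissatisfaction with time spent on clotting control may be describing exactly what the instrument should capture. This stands for items 2, 4, 12 and 15. It does not rescue item 18.

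A reader might infer that half of the controlled group's Treatment Satisfaction score is driven by non-applicability, or that the resulting difference is not experienced quality of life. The documents support neither. Half is the weight of the items, not a demonstrated effect. Controlled VKA patients do have INR results. Protocol 7 says that strict monitoring is unnecessary, not that DOAC patients have no tests. A claim that the effect simply favours the controlled group also fails, because of the conflict over direction in SAP 8.1.

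Two further replies carry some weight. Protocol 9.9 does disclose the VKA origin of the instrument and limits the study to description. SAP 8.1 does report each item by group, so clustering at the floor would be partly visible. It would not be visible by drug, however, and a descriptive figure still needs to mean the same thing in both columns.

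Splitting by drug class helps more than it might seem. It leaves the items no more applicable to DOAC patients, but it confines the problem to their own column.

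**Conclusion.** The point holds for the DOAC patients within the controlled group. Six items may not apply to them, the plan treats those items identically for everyone, and the published columns would hide the consequence. Four of the five dimension scores are touched, Treatment Satisfaction most. The ranges calculated above rest on assumed floor answers, an assumed DOAC share and an assumed applicable answer, so the true size is unknown and could be nil.

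Nor can one conclude that a difference seen only in the standard scores is an artefact. Uncontrolled and controlled VKA patients both have INR results and may differ on these items because of control itself. Their comparison is not affected by this problem. The point justifies an inexpensive addition to the analysis; it does not invalidate the primary outcome.

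**What to change.** In SAP 8.1, keep the standard scores and add one supportive table, labelled as not validated, with dimension scores that omit the six items:

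- Treatment Satisfaction from 14, 21, 27
- Self-efficacy from 5, 9, 24
- Limitations from 3, 6, 7, 11, 22, 23
- Social disturbances from 16, 17, 29, 32
- Stress unchanged

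Show it for uncontrolled VKA, controlled VKA and DOAC as well as the planned columns, and state for each dimension which end is better as scored. For items 2, 4, 12, 15, 18 and 20, report the number and percentage answering 1 and leaving a blank, in the same drug-class columns. These counts test the floor-answer assumption and show whether the missing rule on blanks matters.

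In Protocol 9.9, add that some items may not apply to DOAC patients, and that a difference involving DOAC patients seen only in the standard scores may reflect item applicability or lower monitoring burden. Say there that the controlled-VKA versus uncontrolled-VKA comparison is not affected.

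No new data are needed, since SAP 5.3 already uses the type of anticoagulant. The cost is SAP text, one dimension table, one set of item counts and a short protocol change. The drawback is that the shortened scales, with only three items in two dimensions, lack validation and can only support the standard scores.

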Variables:	
Quality of life: HRQoL will be based on the patients' ratings on Sawicki questionnaire completed during the only study visit. This questionnaire includes 32 items grouped in 5 dimensions – treatment satisfaction, self-efficacy, strained social network, daily hassles and distress. Higher scores indicate lower HRQoL.
 
Uncontrolled patient profile: demographic characteristics (age, gender, work status, life status, etc), CHA2DS2-VASc, HAS-BLED, AF diagnosis date, VKA treatment, time since treatment initiation, time since patient is uncontrolled (if assessable) left ventricular ejection fraction, Kidney function (creatinine clearance), concomitant diseases, concomitant treatments, frequency of visits to the physician, and history of thromboembolic and bleeding events

Data sources:	
Data collection will be limited to those available in the medical records of selected patients and the questionnaire necessary to evaluate the primary objective of the study, of patients in whom a specific therapeutic strategy has already been assigned based on routine practice, and without interference with the physician's prescription habits

Study size:	
It is planned that a total of approximately 330 patients will be recruited for the controlled group and 170 patients will be recruited for the uncontrolled group.
 
Based on such sample size estimates, categorical variables of binomial proportions (e.g. gender) will be estimated with the precision (i.e. width of descriptive 95% confidence interval) described in Table 9.5: 1, according to the prevalence of the attribute.

Data analysis:	
To describe the quality of life among patients controlled and uncontrolled: The primary outcome of the study is the health-related

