### **9.3.2 Outcomes**

#### **9.3.2.1 Primary outcomes**

The primary outcome is the health-related quality of life and will be obtained with the results of the sawicki questionnaire at study visit. The questionnaire to be used is the validated spanish adaptation [9] of the original questionnaire [10]. The questionnaire includes 32 items grouped in 5 dimensions. Patients will estimate the impact of each item on their self-perceived treatment-related quality of life on a scale of 1 (total disagreement) to 6 (total agreement). The 5 dimensions are general treatment satisfaction, self-efficacy, strained social network, daily hassles and distress. A lower score indicates greater higher quality of life and a higher score indicates lower quality of life. The questionnaire is self-completed ([see annex no 3](#)).

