## **8 ANALYSIS OF THE OBJECTIVES**

### **8.1 Primary objective**

***To describe HRQoL in uncontrolled patients treated with VKA and controlled patients treated with VKA or DOAC.***

All the analyses in this section shall be performed for the controlled, uncontrolled and total populations.

Quality of Life shall be based on the patients' assessments, by completing the Sawicki questionnaire during the single study visit. This questionnaire includes 32 items grouped in 5 dimensions: overall treatment satisfaction, self-efficacy, strained social disturbances, daily hassles and distress. The highest scores show less quality of life (validated adapted Spanish questionnaire). The response options for each question are: 1=Not at all, 2=Very slightly, 3=Slightly, 4=Moderately, 5=Quite a lot, 6=Very much. The responses correspond to a quantitative scale from 1 to 6.

Reference: Sanchez GR, Yanes BM, Cabrera MA, Ferrer Garcia-Borras JM, Alvarez NR, Barrera LE. [Cross-cultural adaptation of a questionnaire for measuring the quality of life of patients taking oral anticoagulants]. *Aten Primaria* 2004;34(353):353-9.

The categorical variable to be described is: N and (%):

- Number of patients who completed the questionnaire

The summary score for each dimension is calculated by dividing the total score of the items that comprise each dimension by the number of items included in that dimension (arithmetical mean of the items in question).

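### Higher Sawicki scores are said to mean lower quality of life throughout, but SAP 8.1 scores two of the five primary dimensions the other way round

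*SAP*

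**What the plan says.** Three places state the direction, each for the questionnaire as a whole:

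- Protocol section 4 (Abstract, Variables): "Higher scores indicate lower HRQoL".
- Protocol 9.3.2.1: "a higher score indicates lower quality of life".
- SAP 8.1: "The highest scores show less quality of life".

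SAP 8.1 then defines each dimension score as the mean of its items, answered from 1 (not at all) to 6 (very much). For Treatment Satisfaction (items 4, 12, 14, 15, 21, 27) it adds that "the results of each item in this dimension must be inverted", with the formula n + 1 minus the score and n = 6. Self-efficacy is the "Arithmetical mean of the scores of items 5, 9, 18 and 24", without inversion. Stress, Limitations and Social disturbances are also plain means. For the item-level table the SAP says that "in the inverted items, the inverted value will be provided".

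Protocol 9.7.1 describes a plain mean per dimension and does not mention inversion. Protocol 9.7 leaves further analysis detail to the SAP, so this is a silence and not a competing rule.

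**The concern.** Inverting complaint items turns a scale on which high is bad into one on which high is good. That is the opposite of the direction stated in the same SAP section. The Self-efficacy items ask about confidence and knowledge, so high is good there without any recoding.

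The item and dimension scores by control group are the whole of the primary analysis. If the report repeats the direction sentence above the dimension table, it tells readers that greater satisfaction and greater self-efficacy are signs of poorer quality of life. The group with the better result on those two dimensions would be read as the worse one. The protocol's rationale (section 7) makes this a sensitive place for such an error. It argues that less monitoring may improve quality of life, and Treatment Satisfaction items 4, 12, 15 and 21 concern time spent on control, waiting for results and time lost at the doctor.

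**Working it through.** **Structure.** The SAP's item lists contain 6 + 4 + 10 + 7 + 5 = 32 items and cover items 1 to 32 once each. This reproduces the stated 32 items in 5 dimensions.

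**Item polarity** (SAP 8.1 English text, checked against the Spanish text and anchors in protocol Annex 3; the two agree).

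- Treatment Satisfaction: all six items are complaints. Item 21, for example, is "Está harto de la cantidad de tiempo que pierde en el médico". Raw scores run higher = worse.
- Self-efficacy: all four items are favourable. Item 24, for example, is "Está seguro de poder controlar su tratamiento". Raw scores run higher = better.
- Stress, Limitations, Social disturbances: all 22 items are adverse. Raw scores run higher = worse.

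**Scoring the extremes.** The most favourable patient answers 1 to every adverse item and 6 to items 5, 9, 18 and 24. The least favourable patient does the reverse. An inverted item scores 7 − x. Each cell shows the most favourable / least favourable dimension score.

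| Rule | Treatment Satisfaction | Self-efficacy | Stress | Limitations | Social disturbances |
|---|---|---|---|---|---|
| SAP 8.1 (Treatment Satisfaction inverted) | 6 / 1 | 6 / 1 | 1 / 6 | 1 / 6 | 1 / 6 |
| No inversion (plain mean) | 1 / 6 | 6 / 1 | 1 / 6 | 1 / 6 | 1 / 6 |
| Only Self-efficacy inverted | 1 / 6 | 1 / 6 | 1 / 6 | 1 / 6 | 1 / 6 |
| Both inverted | 6 / 1 | 1 / 6 | 1 / 6 | 1 / 6 | 1 / 6 |

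The stated direction requires 1 / 6 in every column. Under the SAP rule two of five dimensions break it. With no inversion one still does (Self-efficacy), so the SAP's inversion accounts for Treatment Satisfaction only. Only the third rule satisfies the sentence throughout.

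**Item-level table.** Six items are shown inverted and four favourable items are shown raw, so 6 + 4 = 10 of the 32 rows run higher = better. In the six inverted rows the recoded value stands beside unrecoded wording. A high value next to item 21 then means the patient is not fed up.

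**Effect on a group comparison.** Inversion is an exact reflection: the mean becomes 7 − mean and the SD is unchanged. As an illustration with assumed means (not from the documents), take raw complaint means of 2.0 in controlled and 3.0 in uncontrolled patients. The reported Treatment Satisfaction means are 7 − 2.0 = 5.0 and 7 − 3.0 = 4.0. The difference, uncontrolled minus controlled, changes from +1.0 to −1.0, while the stated meaning of a higher score stays the same.

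For a patient who gives the same answer x to all six items, inversion moves the score by |7 − 2x|: 5, 3, 1, 1, 3, 5 points for x = 1 to 6. The shift depends on the answers, so no single figure describes it.

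**The case against.** The strongest reply is that the scoring is sound and only one sentence is too general. Under SAP 8.1 each score rises with what its name says: more satisfaction, more self-efficacy, more stress, more limitations, more social disturbance. The item lists, inversion formula, anchors and item texts are all printed, so the scores can be reproduced. The direction sentence drives no calculation. The study is descriptive, and no total score or test depends on the sentence. Nothing in the documents except that sentence supports inverting the Self-efficacy items, and doing so would make two scores run against their own names.

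Much of this stands. The sentence may be the only fault, no data are lost, and without a total score the dimensions cannot cancel. But correct reading of this table is what a descriptive study delivers, and the written direction contradicts the label on two of five rows. Taking the sentence to describe raw answers does not rescue it, because the raw Self-efficacy items also run the other way. Deferring to the SAP does not help either, since the SAP contradicts itself within one section.

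It is also fair to say that editing the protocol costs more than wording. Protocol 10.1 makes changes introduced by amendment subject to ethics committee and competent authority review and approval.

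**Conclusion.** The inconsistency is real and should be resolved before analysis. Under SAP 8.1, Treatment Satisfaction and Self-efficacy run higher = better, against a direction stated three times without exception. Two of five primary dimensions and 10 of 32 item rows are affected. The harm is a reversed reading of the controlled and uncontrolled columns on those dimensions, not loss or corruption of data.

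The conclusion rests only on the printed item wording, anchors and scoring rule. It does not depend on the assumed means in the illustration. The scoring key of the cited Spanish adaptation is not in the documents, so they cannot settle whether the scoring or the sentence should change.

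**What to change.** Check the scoring in the cited validated Spanish adaptation, then adopt one of the following in both documents.

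- **A. Make the scoring match the sentence.** Leave items 4, 12, 14, 15, 21 and 27 as answered and invert items 5, 9, 18 and 24. Label the two dimensions so that their names do not mislead, for example Treatment Satisfaction (higher = less satisfied).
- **B. Keep the SAP scoring and correct the sentence.** In protocol sections 4 and 9.3.2.1 and in SAP 8.1, give a direction per dimension. Treatment Satisfaction and Self-efficacy: higher = better. Stress, Limitations and Social disturbances: higher = worse.

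Under either option:

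- state in protocol 9.7.1 which items are inverted;
- print the direction beside each dimension in the results table;
- confine any remaining general direction sentence to the dimension scores, because raw items differ in polarity;
- in the item-level table, show raw values beside the item wording or clearly mark each recoded item.

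The cost is wording, table labels and, under A, a few lines of scoring syntax, plus whatever review the protocol changes need under protocol 10.1. No extra data are needed.

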The present study has been designed to describe the HRQoL in patients with non valvular AF receiving conventional VKA but no controlled and those controlled who received VKA or DOAC.

Since the type of patients to be included in this study is that seen in Internal Medicine, i.e. elderly patients, chronically ill, mostly hospitalized, polymedicated, and at high thromboembolic and bleeding risk, the present study will provide valuable data about the HRQoL of these patients regarding their anticoagulation status (controlled or non-controlled).

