### **9.7.1 Main analysis**

The primary outcome of the study is the health-related quality of life as measured by the Sawicki questionnaire. The scores of each individual question will be summarized descriptively in the controlled and uncontrolled patients. In addition, the summary score for each dimension of the questionnaire will be calculated for each patient by dividing the total score by the number of items included in that dimension and summarized in the same way as the individual questions.

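### Sawicki item 23 presupposes a job, yet SAP 8.1 summarises it and counts it as one-seventh of Limitations without using the work status already collected (minor)

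*SAP*

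**What the plan says.** The primary outcome is HRQoL on the Sawicki questionnaire, reported item by item and by dimension; higher scores mean worse HRQoL (Protocol 9.3.2.1 and 9.7.1).

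- **Item.** Item 23 on the Spanish form (Protocol Annex 3) reads "Tiene problemas en el trabajo por sus frecuentes faltas a causa del tratamiento". The SAP renders it as "I have problems at work because of frequent absences caused by my treatment". Neither version is conditional on having a job.
- **Answers.** Annex 3 lists six options, from nothing to a lot, and none for not applicable. SAP 8.1 adds: "The responses correspond to a quantitative scale from 1 to 6".
- **Scoring.** Limitations is the "Arithmetical mean of the scores of items 2, 3, 6, 7, 11, 22, 23". Protocol 9.7.1 obtains a dimension score by "dividing the total score by the number of items included in that dimension"; SAP 8.1 glosses the same rule as an arithmetic mean.
- **Who is included.** SAP 8.1: "All the analyses in this section shall be performed for the controlled, uncontrolled and total populations". Nothing in that section depends on work status.
- **Work status.** It is collected at the single visit (Protocol 9.3) and tabulated by group (SAP 5.2), but has no role in scoring.
- **Population.** Protocol 7 describes "elderly patients, chronically ill, mostly hospitalized, polymedicated, and at high thromboembolic and bleeding risk". Adults from 18 years are eligible (Protocol 9.2.2), and no employment rate is given.
- **Missing values.** Protocol 9.7 rules out imputation and SAP 3.1 says missing values are not counted. Neither says what a blank item does to the score of its dimension.

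**The concern.** A patient without a job cannot have problems at work from treatment absences. The form leaves that patient two natural responses: mark 1, the best possible HRQoL on the item, or leave it blank. In an elderly and largely hospitalised population, many patients may be in this position. The planned item 23 mean then mixes two quantities: how many patients work, and how much treatment disturbs the work of those who do. Only the second is HRQoL.

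The same answers carry one-seventh of the weight in Limitations and pull that score towards better HRQoL whenever the other six items average above 1. In a descriptive study the reported level is itself the result, so a reader should be able to see how much of it comes from an item that does not apply.

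**Working it through.** **Inputs.** From the documents: seven Limitations items, a 1-to-6 scale, and planned groups of 170 uncontrolled and 330 controlled (Protocol 9.5). Assumed, because the documents give no figure:
- p, the share not working: 0.5 to 0.9
- w, the mean of item 23 among workers: 3
- m, the mean of the other six Limitations items: 2 to 4
- non-workers mark 1

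**1. Weight.** The five item lists in SAP 8.1 hold 6 + 4 + 10 + 7 + 5 = 32 items, each used once, which agrees with the stated 32 items in 5 dimensions. Item 23 has weight 1/7 = 14.3% in Limitations.

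**2. Item 23 mean over all who answer** = p × 1 + (1 − p) × w. With w = 3:
- p = 0.5: 0.5 + 1.5 = 2.0
- p = 0.7: 0.7 + 0.9 = 1.6
- p = 0.9: 0.9 + 0.3 = 1.2

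The burden among workers is 3 in every line. Only the employment mix moves the result.

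**3. Limitations for one non-working patient** = (6m + 1)/7. This is 1.86, 2.71 and 3.57 for m = 2, 3 and 4. The difference from m is (1 − m)/7 = −0.14, −0.29 and −0.43.

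**4. Limitations at group level.** If workers score item 23 at the level of their other six items (w = m), the group mean lies p(m − 1)/7 below m:

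| p | m = 2 | m = 3 | m = 4 |
|---|---|---|---|
| 0.5 | 0.07 | 0.14 | 0.21 |
| 0.7 | 0.10 | 0.20 | 0.30 |
| 0.9 | 0.13 | 0.26 | 0.39 |

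Holding workers at w = 3 instead gives [p(m − 1) + (1 − p)(m − 3)]/7. This runs from 0.00 (p = 0.5, m = 2) to 0.40 (p = 0.9, m = 4) and agrees with the table at m = 3.

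**5. Controlled/uncontrolled contrast.** If the non-working share differs by d between groups that are otherwise alike, with w = m, the artificial difference in Limitations is d(m − 1)/7. For d = 0.10 to 0.30:
- smallest: 0.10 × 1/7 = 0.01 (m = 2)
- largest: 0.30 × 3/7 = 0.13 (m = 4)
- at m = 3: 0.03 to 0.09

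With an assumed SD of 1, the standard error of the group difference is √(1/170 + 1/330) = 0.094, so at m = 3 the artefact is below one standard error. For item 23 alone the artificial difference is d(w − 1) = 0.2 to 0.6 at w = 3, so the item row is affected more than the dimension.

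**6. Blanks.** Under SAP 3.1 a blank drops out of the item 23 mean. Whether the patient's Limitations score is then missing or is the mean of six items is not stated. If it were missing, and 50%, 70% or 90% of patients did not work and all left the item blank (assumed), 85, 51 or 17 of 170 uncontrolled and 165, 99 or 33 of 330 controlled patients would keep a score.

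**The case against.** The strongest defence is that the plan follows an instrument it describes as a validated Spanish adaptation, and that a retired patient who marks 1 is answering truthfully: treatment causes no problem at work. On that view there is no bias. The mean of the other six items is a benchmark of the reviewer's own, and no norm, threshold or comparison between dimensions is planned against which Limitations would look too low. Items on housework, cycling, sport and sex life may not apply to some patients either. The item 23 row already shows a median and quartiles, so a floor would be visible, and the study is declared descriptive only (Protocol 9.9).

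Much of this stands. The figures in step 4 are differences between two ways of summarising, not demonstrated errors, and they rest on assumed employment shares. The seven-item score should stay. Two things are not answered. Quartiles that sit at 1 do not separate workers without a problem from patients without work. And for item 23, unlike those other items, the study records a variable that bears directly on whether the question applies.

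A reader might also infer from the fixed divisor that a blank item 23 enters the sum as zero and is still divided by seven. The documents do not support this: Protocol 9.7 excludes imputation, SAP 3.1 does not count missing values, and SAP 8.1 calls the score an arithmetic mean. For the same reason the item is averaged over those who answer it, not over every patient enrolled.

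**Conclusion.** The point holds as a minor one. Item 23 does not apply to patients without a job, the form has no way to say so, and SAP 8.1 ignores the work status that would identify them. The item summary is affected most: under the assumptions above its mean is 2.0 to 1.2 while burden among workers stays at 3. The Limitations level lies 0.07 to 0.39 points below the mean of the six remaining items. Both results depend on an assumed 50% to 90% not working and on non-workers marking 1.

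Two stronger conclusions are not supported. One is that employment materially distorts the comparison of controlled with uncontrolled patients on Limitations: the artefact is 0.01 to 0.13 points even with a 10 to 30 percentage-point difference in non-working share, and no measure of association is planned. The other is that most patients are known not to work: the population description makes this plausible, but no employment figure is given.

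**What to change.** Change SAP 8.1 as follows:

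1. Beside the summary of item 23 over all who answer, add a summary in patients recorded as working, by group, with that N.
2. Keep the seven-item Limitations score. Add one sensitivity row per group for the mean of items 2, 3, 6, 7, 11 and 22.
3. State that a blank item 23 in a non-working patient is treated as missing, in line with SAP 3.1, and that the patient contributes to the six-item row. Say also whether the seven-item score is then missing.

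The cost is a few sentences and a few table rows; no new variable is needed. Work status is taken from the records where available (Protocol 9.3), so the number with it missing should be shown. The downside is that the six-item mean is not the published score, so it should be labelled supportive only.
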